6.13.3 Time to Hemostasis from first Product Application (TTHP)

Time to Hemostasis from first product application (TTHP) (minutes) is defined as the difference between time point of first product application during surgery until time point of reaching hemostasis. Descriptive statistics for TTHP will be shown.

For time-to-event analysis of TTHP, an event is defined as reaching hemostasis. In case no hemostasis has been reached the patient will be censored at 10 minutes. That means that in case that further patches have to be applied the clock for determination of TTHP is

	STATISTICAL ANALYSIS PLAN	FSTAT.01.03
Study Code: HEM-HEM-01-17	Sealantium Medical Ltd.	

prolonged. Kaplan-Meier curves for TTHP for each treatment will be generated. Tabulations will include number and percentage of patients failed and censored, median time to hemostasis with 95% confidence limits, first and third percentile, minimum and maximum time, estimates for 2-minute, 3-minute, 5- minute, 7 minute and 10 minute TTHP hemostasis incidence. Hazard ratio including confidence interval for sFilm-FS versus Tachosil® will be tabulated. Note that to connect correct estimation of hemostasis incidences to the estimations delivered by the survival model, a survival probability denotes the non-occurrence probability of hemostasis.

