Median time to hemostasis from first product application will be estimated using Kaplan-Meier methods; minimum and maximum time will also be reported.

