6 STATISTICAL ANALYSIS METHOD

6.1 General Principles

In general, categorical data will be presented using counts and percentages, whilst

	STATISTICAL ANALYSIS PLAN	FSTAT.01.03
Study Code: HEM-HEM-01-17		Sealantium Medical Ltd.

continuous variables will be presented using the mean, standard deviation, standard error of mean, median, minimum, maximum and number of patients. Minima and maxima will usually be reported to the same level of accuracy as the raw data; means, medians, will be presented to one further decimal place; standard deviations and standard errors will be presented to 2 decimal places more than the raw data. Percentages will be rounded to the nearest integer or with one decimal. In tabulations, denominators for calculation of percentages will be taken as the number of non-missing responses in the specified analysis population and treatment group unless otherwise stated. 95% Clopper-Pearson Confidence Intervals for the means or the percentages will be produced if appropriate to explain the results [1].

Table will display data for each treatment group and overall (=Total column).

All data recorded in the CRF will be listed and sorted by treatment groups, subject number and visits [See Appendix 1].

Considering that the study is designed as phase I/II, in which phase I concerns to the primary endpoint (Safety) and phase II concerns to the preliminary data on effectiveness of sFilm-FS, data will not be presented in the two distinct frames, phase I and phase II.

The probability level for all analyses will be set at 5% and appropriate 95% Confidence Intervals will be produced according to the nature of the variables and will be based on a valid case approach, if so [e.g. percentages will be based on the number of observations available at the specific time point and not based on the number of patients at the visit.

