6.5 Handling of Missing Values

In accordance with the Study Protocol, no substitution or specific approach for missing data will be applied.

	STATISTICAL ANALYSIS PLAN	FSTAT.01.03
Study Code: HEM-HEM-01-17		Sealantium Medical Ltd.

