6.13.4 Time to Hemostasis from Patient Randomization (TTHR)

Time to Hemostasis from patient randomization (TTHR) (minutes) will be collected and displayed with descriptive statistics. TTHR is defined as time from randomization until hemostasis (in case of event) or 10 minutes observation end in case of censoring. Kaplan-Meier curve will be used to estimate the median TTHR in each treatment group. KM parameters and analyses will be tabulated in an analogue manner like in sec. 6.13.3.

6.13.5 Percentage of all Patients who achieved Hemostasis at 10 Minutes after first Product Application

Number and percentage of all patients (patients that achieved hemostasis with a single patch application and patients that required additional patches) that have achieved hemostasis 10 minutes after first product application and therefore did not need to convert to standard of care treatment at the end of these 10 minutes will be tabulated.

Data will be presented with descriptive statistics and 95% confidence intervals of the difference between treatments.

A stratified analyses by one-patch applicants and more than one patch users may be done depending on the results of the BDRM using strata single patch users and additional patch users. In case it is decided to perform a stratified analysis a table will be added to show number/ percentages of patients with one patch and with >1 patches.

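### The plain descriptive statistics for time to hemostasis leave failures out for TTHP and average their censoring time as an observed time for TTHR (SAP 6.13.3, 6.13.4)

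*SAP*

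**What the plan says.** **TTHP.** SAP 6.13.3 defines TTHP as the "difference between time point of first product application during surgery until time point of reaching hemostasis" and then states: "Descriptive statistics for TTHP will be shown". A separate paragraph follows for the survival analysis: "For time-to-event analysis of TTHP, an event is defined as reaching hemostasis", and "In case no hemostasis has been reached the patient will be censored at 10 minutes". That paragraph plans Kaplan-Meier curves, failed and censored counts, a median with confidence limits, hemostasis incidence at 2, 3, 5, 7 and 10 minutes, and a hazard ratio.

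**TTHR.** SAP 6.13.4 states: "Time to Hemostasis from patient randomization (TTHR) (minutes) will be collected and displayed with descriptive statistics". Its definition does cover patients without hemostasis: their time ends with the 10-minute observation. The section does not say whether those 10 minutes start at randomization or at first application.

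**What the summaries contain.** Under SAP 6.1, "continuous variables will be presented using the mean, standard deviation, standard error of mean, median, minimum, maximum and number of patients". The same section puts percentages and confidence intervals on an available-observations basis. Under SAP 6.5, "no substitution or specific approach for missing data will be applied".

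**Protocol.** Protocol 14.8.2 gives the method for TTHP: "Median time to hemostasis from first product application will be estimated using Kaplan-Meier methods; minimum and maximum time will also be reported". TTHR is to be collected but not used as an endpoint. SAP 9.2 records that its analysis was added.

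**The concern.** A time that exists only for patients who reach hemostasis cannot be summarised by a plain mean or median without conditioning on success. A patient who would have been slow stays in the table if the bleeding stops and leaves it if it does not. The more often a product fails in difficult bleeds, the shorter its achievers-only mean tends to be.

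For TTHR the fault differs. The failure stays in, but its value is only a lower limit on a time that was never observed. The mean and SD treat it as an observed time.

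At stake is a secondary efficacy endpoint. The report would carry two medians per arm for time to hemostasis, one plain and one Kaplan-Meier. They can disagree, and nothing says which to read. With about 15 patients per arm, a few failures are enough to move the plain mean.

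**Working it through.** **Inputs from the documents.** 15 patients per arm (Protocol 14.1, SAP 3.4). Assessments at 2 minutes (sFilm-FS only), 3, 5, 7 and 10 minutes after application (Protocol 11.1.3). TTHP censored at 10 minutes in the survival analysis (SAP 6.13.3). The documents give no distribution of times and no failure rate, so all times and rates below are assumptions.

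**The plan's own figure.** Nothing is stated for TTHP or TTHR. The nearest figure is the exact interval in Protocol 14.8.2 for 80% of 15 patients, given as 52% to 96%. Clopper-Pearson for 12/15 gives 51.9% to 95.7%, so it reproduces.

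**Step 1: achievers only (TTHP).** Assume:
- Arm A: 6 dry at 3 min, 4 at 5, 3 at 7, 2 at 10; no failures.
- Arm B: 6 dry at 3 min, 4 at 5, 1 at 7; 4 never.

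| Summary | Arm A | Arm B |
|---|---|---|
| Achievers-only mean | (18+20+21+20)/15 = 5.27 | (18+20+7)/11 = 4.09 |
| Achievers-only median | 5.0 | 3.0 |
| Kaplan-Meier median | 5 | 5 |
| Hemostasis by 10 min | 15/15 = 100% | 11/15 = 73% |
| Mean with failures set to 10 | 79/15 = 5.27 | (45+40)/15 = 5.67 |

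On the plain table B looks 1.18 min faster on the mean and 2 min faster on the median. On Kaplan-Meier the medians are equal and B has the lower incidence.

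**Step 2: more failures, shorter mean.** With 6 failures in B (6 dry at 3 min, 3 at 5), the achievers-only mean is 33/9 = 3.67. With 8 failures (6 at 3 min, 1 at 5), it is 23/7 = 3.29, while 10-minute incidence is 7/15 = 46.7%, so the Kaplan-Meier median is not reached.

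**Step 3: a milder case.** Let 12 of 15 be dry at 3 min in both arms, matching the protocol's 80% example. In one arm the other 3 never stop; in the other they stop at 9 min (not a scheduled time, but assessments after re-treatment may fall elsewhere). Means: 36/12 = 3.0 against (36+27)/15 = 4.2 min. All medians, plain and Kaplan-Meier, are 3 min, so only the mean misleads here.

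**Step 4: expected direction.** Assume cumulative hemostasis at 3/5/7/10 min of 60/80/90/95% in A and 60/70/73/75% in B.
- Achievers-only expectation, A: (0.60×3 + 0.20×5 + 0.10×7 + 0.05×10)/0.95 = 4.00/0.95 = 4.21 min.
- Achievers-only expectation, B: (0.60×3 + 0.10×5 + 0.03×7 + 0.02×10)/0.75 = 2.71/0.75 = 3.61 min.

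B has five times the failures (25% against 5%) and the shorter mean. In 20,000 simulated trials of 15 per arm, B has the lower achievers-only mean in about 81%. With failures set to 10 min the share is about 22%. Using the sample median with failures ranked last, it is about 17%.

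**Step 5: TTHR.** Take the Step 1 data and assume 2 minutes from randomization to application in every patient. Arm A: (79 + 15×2)/15 = 109/15 = 7.27. The 11 achievers in B contribute 45 + 11×2 = 67.
- If the 10 minutes run from application, each failure scores 12: (67+48)/15 = 7.67.
- If they run from randomization, each failure scores 10: (67+40)/15 = 7.13.

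Under the second reading a failure (10) beats a patient who is dry 10 minutes after application (12), and B again looks faster than A. Under the first reading the order is right, but 7.67 is only a lower limit.

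**The case against.** The strongest reply is that the same plan already shows the failures. SAP 6.13.3 keeps the Kaplan-Meier output and censored counts. SAP 6.13.1, 6.13.5 and 6.13.6 report hemostasis by time point, hemostasis at 10 minutes and treatment failure. SAP 6.1 puts the number of patients in each continuous summary, so 11 would stand beside 15. Safety is primary, no hypothesis is tested, and SAP 6.6 calls all results exploratory. This stands and limits the harm. It does not repair the plain mean or say which median to read.

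Four stronger readings are tempting, and the documents do not support them:
- *TTHR also drops its failures.* It does not; SAP 6.13.4 gives them a value.
- *The SAP states that failures are excluded from the TTHP summary.* No sentence says so. The exclusion follows from the definition, the scope of the censoring rule and the absence of substitution. The table shells are separate documents and may carry a label or footnote.
- *The SAP made a hidden departure from a protocol that allowed only Kaplan-Meier.* Protocol 14.8 and 14.8.2 provide for descriptive efficacy analyses, Protocol 14.6 lets the SAP contain further analyses of the endpoints, and SAP 9.2 discloses the TTHR addition.
- *The reversal is a forecast for this trial.* The times and failure rates are constructed.

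It is also fair that an achievers-only summary is legitimate when it is labelled as one.

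**Conclusion.** The point holds. For TTHP, the SAP's own definitions lead to a plain summary of achievers only, which can favour the arm with more failures. For TTHR, they lead to a mean in which a censored time counts as an observed one, with an unstated time origin. In the illustrations the TTHP distortion is 1.2 min, both with 4 failures against none (4.09 against 5.27) and in the milder case with 3 (3.0 against 4.2). The TTHR order depends on the unstated origin (7.67 or 7.13 against 7.27). These sizes rest on assumed times, failure rates and a 2-minute application delay. With equal failure patterns the comparison between arms is little affected, and with no failures the problem disappears. The change is worth making because it costs little, but no decision, sample size or stopping rule depends on these summaries.

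**What to change.** 1. In SAP 6.13.3 and 6.13.4, drop the plain mean, SD, SEM and median. Summarise both times by the Kaplan-Meier median and quartiles already planned, with failures censored, plus minimum and maximum observed time and the number not achieving hemostasis by 10 minutes. SAP 6.13.3 writes percentile where quartile seems meant; correct that too.
2. If a simple table is wanted, either rank failures as longer than 10 minutes and give the median and quartiles over all patients, with no mean, or label the table as achievers only and print number achieved over number treated beside it.
3. In SAP 6.13.4, state whether the 10 minutes that end a censored TTHR run from randomization or from first application. The TTHR Kaplan-Meier analysis needs this as well.

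Cost: a sentence or two in each section and one descriptive table lost or relabelled. No new data are needed.

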The time of application will be considered **TP-01** and will be recorded as such. If the sFilm-FS is to be used, do not moisten the product prior to application, as the product will be activated immediately. TACHOSIL® should be used in accordance with the approved Prescribing Information.

Following product application, manual compression will be applied and will be maintained for at least 2 minutes for sFilm-FS and for at least 3 minutes for TACHOSIL®, until examination of TBS. The Investigator may use a surgical sponge (laparotomy pad or surgical gauze) to assist in providing adequate pressure to stem all bleeding over the entire treated surface area at the TBS. Hemostasis will then be assessed by carefully releasing manual compression and removing the surgical sponge (if used) without disturbing the hemostasis product. The product unit should be left in place once it adheres to organ tissue.

In case hemostasis is not achieved within 2 minutes (for sFilm-FS) or 3 minutes (for TACHOSIL®), the surgeon will wait 2 additional minutes applying additional pressure on the gauze before carefully releasing manual compression and checking again.

Hemostasis will be assessed at 2 (for sFilm-FS only), 3, 5, 7 and 10 minutes following product application. These time points will be recorded as **TP-02**, **TP-03**, **TP-05**, **TP-07** and **TP-10** respectively.

Re-treatment: If the surgeon is not satisfied with the placement of the patch, or if hemostasis is not achieved, or if during the subsequent observation period bleeding requiring treatment recurs, the

Investigator may decide to apply an additional product unit as specified above. In this case, the already applied product unit should not be removed, unless it did not adhere to the TBS.

The time point of product re-application will be recorded as **TPR-01**. After re-treatment application, manual compression must be applied for at least 2 (for sFilm-FS) or 3 minutes (for TACHOSIL®, as described above. Hemostasis will then be assessed following product re-application at any time-points within the original 10 minutes observation period (**TPR-02**, **TPR-03** or other) and until site closure. A minimum of 5 minutes observation period at the TBS has to take place before site closure. The time followed by 5-minutes observation period to assess hemostasis will be recorded.

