14.8.2 Secondary Endpoints

The secondary endpoints of the study are:

- Proportion of patients achieving hemostasis at TBS (absence of bleeding) at 2 (for sFilm-FS product only), 3, 5, 7 or 10 minutes following first product application, without the occurrence of re-bleeding starting from 10 minutes after product application and until the completion of surgical closure.
- Incidence of re-treatment (one or more additional patch of sFilm-FS or TACHOSIL[®]) at the TBS at the different time points (2 for sFilm-FS, 3, 5, 7, 10 minutes from first product application).
- Time to Hemostasis from first product application (TTHP). Time to Hemostasis from patient randomization (TTHR) will be collected as well but will not be used as endpoint.
- Percentage of total patients (patients that achieved hemostasis with a single patch application and patients that required additional patches) that have achieved hemostasis 10 minutes after first product application and therefore did not need to convert to standard of care treatment at the end of these 10 minutes.
- Incidence of treatment failure, based on pre-defined treatment failure criteria (see definition in Section 11.1.3 of the protocol).
- Incidence of transfusion requirements in the 6 months follow up period.

Descriptive efficacy analyses will be summarized separately by treatment arm.

Primary analyses will calculate the proportion of patients achieving hemostasis at 3 minutes among the sFilm-SF treatment arm. With 15 patients randomized to sFilm-SF, reasonable confidence intervals (CI) can be estimated. For example, if 80% of the patients achieve hemostasis at 3 minutes (similar to a TACHOSIL[®] reported values of 81% for this endpoint), the accompanying 95% confidence interval (CI) is 52% to 96% (using exact confidence limits). This CI provides evidence that greater than 52% of patients with similar conditions will achieve hemostasis at 3 minutes. This will also be reported for the 15 patients randomized to the TACHOSIL[®] arm. There will be no formal comparison between the two-arms.

Similarly, proportions of patients and corresponding 95% CIs will be estimated for all of the following, separately by treatment arm:

- achieving hemostasis at TBS at each remaining time point,
- incidence of re-treatment (separately by time),
- incidence of treatment failure (as defined in Section 11.1.3), and
- incidence of transfusion requirements.

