⁴ Urine analysis tests include: specific gravity, pH, glucose, protein, blood, ketones, microscopic examination.

⁵ A serum sample will be collected and stored at -70°C for possible future viral safety testing.

⁶ Measurement of levels of antibodies against Human Fibrinogen and Human Thrombin. For this purpose, a serum sample will be collected and stored at -70°C for testing at the end of the study.

⁷ Additional MRI will be performed throughout the study if the investigator identifies signs and symptoms of unanticipated or unexpected persistent inflammatory response, or unexplained abdominal pain or other symptoms (for instance signs of adhesions, bowel obstruction, etc.).

⁸ Operative/surgical information include OR time, procedure time, time from liver resection/incision to initiation of fascial closure, drain usage, estimated blood loss, cell salvage use, transfusion information (if applicable), length of stay (ICU and overall LOS).

⁹ Intra-operative details include hepatic parenchyma classification type (normal or abnormal, steatotic, cirrhotic or other), Investigator description of the TBS (area, density, arterial/venous/mixed, intensity of flow), alternative methods used to achieve hemostasis (if applicable), estimated TBS treated area and total resected area, number of product units applied at the TBS and at other areas rather than the TBS, incidence of post-operative bile leaks requiring intervention, hepatic segment information (anatomic resection/non-anatomic resection).

¹⁰ Patients will be monitored for absence of bleeding at 2, 3, 5, 7, and 10 minutes after product application and thereafter, before closing the site.

¹¹ Assessments to be taken daily from one day after surgery (D1) until hospital discharge (D-HD).

	STATISTICAL ANALYSIS PLAN	FSTAT.01.03
Study Code: HEM-HEM-01-17		Sealantium Medical Ltd.

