6.13.1 Proportion of Patients achieving Hemostasis at TBS

For each patients achievement of hemostasis at TBS (absence of bleeding) at 2 (for sFilm-FS product only), 3, 5, 7 or 10 minutes following first product application will be derived. No occurrence of re-bleeding starting from 10 minutes after product application and until the completion of surgical closure must happen.

This variable, as being a time-profile in the efficacy response, will be considered to suggest a superiority in the efficacy of study drug versus control treatment. Since this is an exploratory proof of concept study and no hypothesis of extent in the difference between treatment groups a priori has been defined, we estimate the differences in the proportion of patients achieving at each time points hemostasis at TBS by the calculation of the exact 95% confidence interval (Clopper-Pearson exact method, considering the sample size) at each time point. This measure gives also a precision of the difference between treatments observed.

Beside Clopper-Pearson confidence intervals number and percentage of patients achievement of hemostasis at TBS will be tabulated by time point. The tabulation will also differ between first application and re-applications.

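### TTHP hazard ratio (SAP 6.13.3) compares an arm first examined at 2 minutes with one first examined at 3, so on the listed look times it favors sFilm-FS even if the products are identical

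*SAP*

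**What the plan says.** Protocol 11.1.3 sets the looks by arm: "Hemostasis will be assessed at 2 (for sFilm-FS only), 3, 5, 7 and 10 minutes following product application". Compression is held for at least 2 minutes with sFilm-FS and at least 3 with TACHOSIL before the site is examined. SAP 6.13.1 repeats the 2-minute restriction to sFilm-FS.

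Two other statements do not fit that list. If the first look fails, Protocol 11.1.3 says "the surgeon will wait 2 additional minutes applying additional pressure on the gauze before carefully releasing manual compression and checking again". That puts the second sFilm-FS look at 2 + 2 = 4 minutes, not 3. Footnote 10 of the schedule, in the protocol and in SAP 3.1, has no arm restriction: "Patients will be monitored for absence of bleeding at 2, 3, 5, 7, and 10 minutes after product application".

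SAP 6.13.3 defines the TTHP event as reaching hemostasis, censors at 10 minutes, and asks for Kaplan-Meier curves by arm, "estimates for 2-minute, 3-minute, 5- minute, 7 minute and 10 minute TTHP hemostasis incidence", and the "Hazard ratio including confidence interval for sFilm-FS versus" TACHOSIL. It names no model or tie method and does not deal with the different first looks. SAP 6.13.4 carries the same outputs over to time from randomization (TTHR).

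Protocol 14.8.2 planned less: "Median time to hemostasis from first product application will be estimated using Kaplan-Meier methods; minimum and maximum time will also be reported", and "There will be no formal comparison between the two-arms". SAP 9.1 and 9.2 record changes, including the added TTHR analysis, but not the hazard ratio.

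**The concern.** On the listed looks, a TACHOSIL patient whose bleeding stopped under compression before 2 minutes is recorded at 3. The same patient on sFilm-FS is recorded at 2. The Cox risk set at 2 minutes contains all 15 TACHOSIL patients, none of whom can have an event there. The hazard ratio therefore mixes the look schedule with any product effect, and the 2-minute Kaplan-Meier incidence for TACHOSIL shows an unmeasured quantity as 0%.

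SAP 6.13.1 says the hemostasis time profile "will be considered to suggest a superiority in the efficacy of study drug versus control treatment". A hazard ratio above 1 in the next subsections could easily be read the same way.

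**Working it through.** **Inputs from the documents.** 15 patients per arm (SAP 3.4). 81% dry at 3 minutes, the TACHOSIL value in Protocol 14.8.2, used here for both arms. Looks at 2, 3, 5, 7, 10 (sFilm-FS) and 3, 5, 7, 10 (TACHOSIL). Censoring at 10 minutes. The protocol's own figure reproduces: 80% of 15 is 12/15, and the Clopper-Pearson interval is 51.9% to 95.7%, against a stated 52% to 96%.

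**Assumptions.** Identical products. F2, the proportion dry by 2 minutes, is not in the documents and is varied. Later proportions are set at 88/92/95% by 5/7/10 minutes.

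**Direction.** Let F3 be the proportion dry by 3 minutes and n the number per arm. Log-rank observed minus expected for sFilm-FS, at a true ratio of 1:
- at 2 minutes: nF2 − nF2/2 = nF2/2
- at 3 minutes: n(F3 − F2) − n(2F3 − F2)(1 − F2)/(2 − F2) = −nF2(1 − F3)/(2 − F2)
- after 3 minutes the risk sets are equal and contribute 0

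The sum is nF2(2F3 − F2)/[2(2 − F2)]. It is positive whenever F2 > 0, because F3 ≥ F2. With n = 15, F2 = 0.40 and F3 = 0.81: 15 × 0.40 × 1.22 / 3.2 = 2.29 excess events. The early excess is only partly offset at 3 minutes.

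**Exact case.** 12/15 dry at the first look in each arm, the other 3 censored. At 2 minutes there are 12 sFilm-FS events with 15 v 15 at risk. At 3 minutes there are 12 TACHOSIL events with 3 v 15 at risk. The Breslow score equation is HR/(HR + 1) + HR/(HR + 5) = 1, so HR² = 5 and HR = 2.24. The 95% CI is 0.94 to 5.32 (Breslow) or 0.98 to 5.09 (Efron). The 2-minute incidence is 80% v 0%.

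**Simulation.** 6,000 trials per row, identical products, 15 per arm. Infinite ratios (up to 4% of trials at 80%) are kept in the median but not counted as intervals above 1.

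| Dry by 2 min (assumed) | Median HR, listed looks, Breslow / Efron | CI wholly above 1, Breslow / Efron | Common 3, 5, 7, 10 grid | Re-check looks (sFilm-FS 2, 4, 7, 10), Breslow | Re-check looks moved to common grid |
|---|---|---|---|---|---|
| 80% | 2.10 / 2.13 | 39% / 44% | 1.00 | 2.03 | 0.98 |
| 60% | 1.68 / 1.64 | 20% / 26% | 1.00 | 1.37 | 0.86 |
| 40% | 1.40 / 1.35 | 5% / 12% | 1.00 | 0.96 | 0.71 |
| 20% | 1.19 / 1.15 | 0.4% / 5% | 1.00 | 0.67 | 0.56 |

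For the re-check columns, the proportion dry by 4 minutes is set at 84.5%, midway between 81% and 88%. A separate solution on expected counts, with 97% dry by 10 minutes, gives Breslow ratios of 1.00, 1.06, 1.18, 1.38 and 1.95 at F2 = 0, 1/15, 0.20, 0.40 and 0.80. At F2 = 0.40 the ratio is 1.23 if F3 is 60% and 1.49 if F3 is 95%.

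**Median.** The sFilm-FS median is 2 minutes only if at least 8 of 15 are dry at the 2-minute look. The binomial probability is 99.6%, 78.7%, 21.3% and 0.4% at F2 = 80, 60, 40 and 20%.

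**The case against.** The strongest reply is that shorter compression is part of the sFilm-FS regimen. If the target is time to declared hemostasis under each regimen, an earlier permitted release is a real difference, and the ratio summarizes it. This stands for the per-arm curves and medians. It does not rescue a ratio that counts TACHOSIL patients as at risk when they cannot be observed, nor a 0% for a time point nobody assessed. The SAP also does not say that the regimen comparison is its target.

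Other points stand in part:
- The direction is secure only on the listed looks; under the re-check rule it can reverse. That is a further reason not to report the ratio until the schedule is settled.
- The sizes are illustrative. The simulation has no re-treatment or re-bleeding, and the SAP does not say whether TTHP is a look time or a clock time. TACHOSIL is not examined before 3 minutes on either reading.
- The 80% row and the exact case assume almost nobody becomes dry between 2 and 3 minutes. At 20% the effect is small.
- SAP 6.6 calls all results exploratory, and 6.13 excludes p-values. The superiority sentence in 6.13.1 concerns proportions, so extending it to the ratio is inference.
- Protocol 14.6 allows the SAP to add analyses, so the missing entry in 9.1 is a matter of record-keeping.
- Footnote 10 is a schedule summary, and the other statements of the 2-minute point restrict it to sFilm-FS. It is the weaker of the two look-time conflicts.

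**Conclusion.** The concern holds and should be fixed. On the listed looks, the hazard ratio for identical products exceeds 1 in expectation whenever any sFilm-FS patient is dry at 2 minutes; a single trial can still fall below 1 by chance. The median ratio runs from about 1.2 to 2.1 as the assumed 2-minute rate goes from 20% to 80%, with 81% dry at 3 minutes. The direction is the same under both tie methods, and the bias disappears on a common first look. If surgeons followed the re-check rule, the ratio could run from 2.03 down to 0.67, so even its direction is not fixed by the plan. The safety primary endpoint and the per-arm descriptions are unaffected.

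**What to change.** 1. Reconcile the look times: the listed times against the re-check rule in Protocol 11.1.3, and footnote 10 in both documents. State in the SAP which recorded time points count as looks, and whether TTHP is a look time or a clock time.
2. Delete the hazard ratio from SAP 6.13.3 and, by extension, 6.13.4.
3. If a between-arm time analysis is kept, use the common grid 3, 5, 7, 10 minutes if the listed looks were followed. Count 2-minute sFilm-FS events at 3, and state how a patient dry at 2 but bleeding at 3 is classified. If the listed looks were not followed, use interval-censored methods with the actual look times, because the common grid is then not neutral (0.56 to 0.98 above).
4. Tabulate the 2-minute figure for sFilm-FS only and mark TACHOSIL as not assessed. Give the earliest observable time by arm beside each median.
5. List any retained hazard ratio in SAP 9.1, with its model and tie handling.
6. In SAP 6.13.4, clarify that the 10-minute end of observation runs from first application, although the TTHR clock starts at randomization.

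The cost is SAP wording and a short derivation; interval censoring also needs the recorded look times. The downside is that sFilm-FS gets no between-arm credit for its 2-minute look, although the shorter compression is part of its regimen.
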